6.5.2. Criteria for Permanent Discontinuation of Study Drug

The occurrence of unacceptable toxicity not caused by the underlying disease will require that the study drug be permanently discontinued. Unacceptable toxicity is defined as follows:

- The occurrence of an AE that is related to study treatment that, in the judgment of the investigator or the sponsor's medical monitor, compromises the participant's ability to continue study-specific procedures or is considered to not be in the participant's best interest.
- A worsening of AD that requires treatment with a prohibited concomitant medication.
- A persistent AE requiring a delay of therapy for more than 2 weeks without resolution of the AE (unless a greater delay has been approved by the sponsor).

See Section 7.1.2 for discontinuation procedures.

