6.6.3. Prohibited Medications and Procedures

[Table 8](#) lists prohibited medications that are not to be used from the defined washout periods prior to the run-in period through the last study visit.

Participants who start prohibited medications or therapies that have been demonstrated to be effective for treatment of AD/pruritus during the study will be withdrawn from the study.

Participants who start prohibited medications or therapies for other reasons during the study may be withdrawn from the study if an impact on efficacy assessment or safety of the participants is expected. If in any doubt, investigators are advised to discuss medications with the medical monitor.

Participants who present with a worsening of AD that requires treatment with a prohibited concomitant medication will have the study drug permanently discontinued.

Table 8: Prohibited Therapies or Procedures

Prohibited Medications, Products, and Procedures	Washout Period Prior to:	
	Run-In Period	Day 1
Dupilumab	26 weeks	—
Any marketed or investigational biological agent that may impact the course of AD or its assessments	12 weeks or 5 half-lives (whichever is longer)	—
Major surgery	—	8 weeks
JAK inhibitor (systemic or topical)	4 weeks	—
Nonbiological investigational product or device	4 weeks	—
Live-attenuated vaccine	4 weeks or 5 half-lives (whichever is longer)	—
Systemic corticosteroid (oral/injectable) ^a	4 weeks	—
Systemic treatment (other than biologics) that could affect AD and/or pruritus ^b	4 weeks	—
PUVA treatment, UV-B phototherapy (including tanning beds) or excimer laser, excessive sun exposure	4 weeks	—
Topical medicated treatment that could affect AD and/or pruritus ^c	2 weeks	—
Doxepin	2 weeks	—
Oral, sedative, H ₁ antihistamine ^d	2 weeks	—
Anticoagulant medication ^e	—	2 weeks
Antibiotics (systemic or topical) for infected AD	2 weeks	—

^a Intranasal corticosteroids and inhaled corticosteroids are allowed. Eye and ear drops containing corticosteroids are also allowed.

^b For example, retinoids, calcineurin inhibitors, PDE-4 inhibitors, methotrexate, cyclosporine, hydroxycarbamide (hydroxyurea), azathioprine, interferon-gamma, or opioids (agonist, partial agonist-mixed, or antagonist).

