6.2 Handling of Dropouts or Missing data

No imputation will be made for efficacy data. See [Appendix 2](#) for handling of completely or partially missing dates for prior and concomitant medications and adverse events.

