12.2.3 Minimal Clinically Important Difference

The minimal clinically important difference (MCID) corresponds to an achievement of ≥ 2 -grade reduction in PP-NRS and mPP-NRS from baseline.

The MCID will be analyzed as follow:

- Time to MCID for PP-NRS (≥ 2 -grade reduction in PP-NRS from baseline).
- Time to MCID for mPP-NRS (≥ 2 -grade reduction in mPP-NRS from baseline).

The time to MCID will be defined as the time from the date (time) of first dose to the date (time) of first occurrence of MCID. The time to MCID for the PP-NRS will be reported in days, and the time to MCID for the mPP-NRS will be reported in hours.

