12.2.5 Secondary Endpoints Analysis

Descriptive statistics will be presented for all secondary efficacy endpoints, by visit and timepoint (if applicable). The change from baseline and percent change from baseline in PP-NRS, mPP-NRS and IGA, and proportion endpoints for PP-NRS, mPP-NRS, and IGA-TS, will be analyzed descriptively at each visit. The 95% CI will be provided for the mean change, percent change and the proportions (using the Clopper-Pearson method). For proportion endpoints, percentages will be based on the number of participants with a response at the specified visit and timepoint.

The proportion of participants achieving an IGA score of 0 or 1 and associated 95% CI (using the Clopper-Pearson method) will also be reported descriptively.

The time to MCID will be analyzed using Kaplan Meier estimation for PP-NRS and mPP-NRS. A participant will be considered censored if he has not met the event of interest at the end of the study or if the participant is lost to follow up at last observation. Those participants will be censored at their last available mPP-NRS or PP-NRS assessment date or time. Survival curves will also be presented.

A line graph presenting the value and a line graph presenting the change from baseline in mPP-NRS over time will be produced. The value and change from baseline in PP-NRS over time and value and change from baseline in IGA will be presented similarly.

	STATISTICAL ANALYSIS PLAN, Version Final v1.0
Protocol Number: INCB 18424-901	Sponsor: Incyte Corporation
Study Title: An Open-Label, Single-Arm Study to Evaluate the Effect of Ruxolitinib 1.5% Cream on Itch in Adult Participants With Atopic Dermatitis (SCRATCH-AD)	

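### For PP-NRS, the SAP has no rule for participants withdrawn as treatment failures before a first MCID; if any occur, censoring them makes the Kaplan-Meier curve overstate attainment

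*SAP*

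**What the plan says.** SAP 12.2.3 defines the endpoint: "The time to MCID will be defined as the time from the date (time) of first dose" to the first reduction of at least 2 grades from baseline, in days for PP-NRS and in hours for mPP-NRS. SAP 12.2.5 sets the method: "The time to MCID will be analyzed using Kaplan Meier estimation for PP-NRS and mPP-NRS". On censoring it says "A participant will be considered censored if he has not met the event of interest at the end of the study", adds loss to follow-up, and then: "Those participants will be censored at their last available mPP-NRS or PP-NRS assessment date or time". The reason for leaving plays no part. SAP 6.2 adds "No imputation will be made for efficacy data".

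The protocol creates exits tied to the outcome. Section 6.5.2 lists as a ground for stopping study drug "A worsening of AD that requires treatment with a prohibited concomitant medication". Section 6.6.3 repeats it: "Participants who present with a worsening of AD that requires treatment with a prohibited concomitant medication will have the study drug permanently discontinued". A separate sentence in 6.6.3 goes further: participants who start prohibited therapies shown to be "effective for treatment of AD/pruritus during the study will be withdrawn from the study". That last sentence is the one that ends the daily PP-NRS.

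**The concern.** Kaplan-Meier treats a censored participant as having the same later chance of the event as those still followed at that time. That is hard to defend for someone taken out because the disease got worse or needed another treatment. If the person had not reached MCID, the exit is evidence that MCID was not coming on this treatment, yet the estimator credits them with a share of the later responses.

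No other planned analysis offsets this. Efficacy data are not imputed. The responder proportions in SAP 12.2.5 are based only on participants with a score at the timepoint, so they give no conservative cross-check. No competing-event, nonresponder or sensitivity analysis of time to MCID is planned, and the per protocol set only removes participants.

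Time to MCID is a listed secondary endpoint with its own curve. In a single-arm study no comparator curve carries the same distortion, so the absolute percentage read off the curve is the result.

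**Working it through.** **The plan's own figure.** The plan gives no number for time to MCID. Its one relevant calculation is the sample size in SAP 5.1 (SD 1.64, precision 0.57, 95% two-sided, 10% missing). It reproduces: (1.96 × 1.64 / 0.57)² = 31.8, rounded up to 32; 32 / 0.9 = 35.6, rounded up to 36. It concerns the Day 2 mean change and is not affected by this point. The current total of about 48 is used below.

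**Formula.** Let N be the number treated, R the number who reach MCID by Day 29, m those who reach it before the exits, and k the failure exits without MCID, placed for simplicity at one time. With no other early censoring:

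- Competing-event estimate at Day 29 = R / N.
- One minus Kaplan-Meier = 1 − [(N − m) / N] × [(N − R − k) / (N − m − k)].

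The two agree when k = 0, and also when m = R (exits after the last response). Otherwise Kaplan-Meier is higher. The largest gap is at m = 0, where Kaplan-Meier becomes R / (N − k).

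**Assumptions, not from the documents.** N = 48, R = 34 (70.8%), response times exponential with mean 6 days, exits on Days 5 to 14 by participants who would never respond. At the midpoint, Day 9.5, exp(−9.5/6) = 0.205, so about 7 of the 34 responses are still to come and m = 27.

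| Exits k | One minus Kaplan-Meier, hand check | Excess over 70.8% | Excess, simulated with exits spread over Days 5 to 14 | Upper bound, 34/(48 − k) |
|---|---|---|---|---|
| 0 | 70.8% | 0 | 0 | 70.8% (0) |
| 1 | 1 − (21/48)(13/20) = 71.6% | +0.7 | +0.8 | 72.3% (+1.5) |
| 2 | 1 − (21/48)(12/19) = 72.4% | +1.5 | +1.7 | 73.9% (+3.1) |
| 4 | 1 − (21/48)(10/17) = 74.3% | +3.4 | +3.6 | 77.3% (+6.4) |
| 6 | 1 − (21/48)(8/15) = 76.7% | +5.8 | +6.0 | 81.0% (+10.1) |

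The simulated column rests on 2,000 to 3,000 trials per scenario. With R = 38 and four exits the simulation gives 84.0% against 79.2% (+4.8).

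**Wider range.** Varying R over 29, 36 and 41 of 48, fast or even onset, and exits at Day 3, 8, 15 or 28, the excess over the Aalen-Johansen estimate is 0 points with no exits, 0.1 to 1.8 with one, 0.2 to 3.7 with two, and 0.7 to 9.9 with five. For example, with 36 responders, fast onset and five exits at Day 8, Kaplan-Meier gives 80.6% against 75.0%. It is never below the competing-event estimate.

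**Quantiles.** In the four-exit simulations the mean median time is 8.65 against 8.79 days (R = 34) and 7.47 against 7.56 days (R = 38), a shift of about 0.1 day. Upper quantiles can move more. With R = 34, 70% of 48 is 33.6, so the 70% point is the 34th and last response. Its expected time is 6 × (1 + 1/2 + … + 1/34), about Day 25. With four exits censored near Day 9.5, Kaplan-Meier crosses 70% at the 33rd response, about 6 days sooner. That quantile rests on one or two participants.

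**The case against.** The strongest case against is that the effect may be negligible. No document gives a rate of withdrawal for worsened AD. The nearest figure, in Protocol 2.2.2, is dermatitis atopic reported as a TEAE in 12 participants (1.9%) in the first part of INCB 18424-303; 1.9% of 48 is about one person. It is a poor proxy, because it counts events rather than withdrawals, but it does not suggest four to six exits. Recent flares are excluded at entry and treatment lasts about 28 days. One or two exits add about 0.8 to 1.7 points, while sampling error at 70.8% of 48 is 1.96 × √(0.708 × 0.292 / 48), about ±13 points. SAP 7.1 already tabulates reasons for study discontinuation, so a reader could bound the bias. All of this stands and limits the weight of the point.

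It can also be said that censoring at failure targets a hypothetical question, namely response had nobody left for failure. That is a legitimate choice, but the SAP does not state it, and it would still need the doubtful assumption that leavers resemble stayers.

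A reader might infer more than the documents support:

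- **That the SAP explicitly orders treatment failures to be censored.** It names only the end of the study and loss to follow-up, and Protocol 7.3 defines the latter as missed visits and no contact. Failure withdrawals are censored by default.
- **That everyone whose AD worsens is lost to the curve.** Sections 6.5.2 and 6.6.3 stop the drug, and Protocol 7.1.2 lets those who withdraw consent for treatment alone continue efficacy assessments. Anyone who does so stays in the risk set.
- **That the curve is bound to be biased in the drug's favour.** There is no effect without such exits. An exit after a first 2-grade drop is already an event, and the first qualifying score among up to 28 daily ones is enough.
- **That mPP-NRS is affected.** Its last score is 12 hours after the first application, so these withdrawals can hardly touch it.

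**Conclusion.** The point holds conditionally and for the PP-NRS curve only. If participants are withdrawn for worsened AD or a prohibited AD or itch therapy before a first MCID, and before the last observed response, the default censoring raises the reported share reaching MCID; it cannot lower it. The likely size, with one or two exits, is a point or two at Day 29; larger values need exit counts for which the documents give no support. All figures assume that those who leave would not have responded. The endpoint is secondary and descriptive. This is a gap worth closing cheaply, not a flaw that threatens the trial's conclusions.

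**What to change.** In SAP 12.2.5, for PP-NRS time to MCID:

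- Treat withdrawal for AD worsening, lack of efficacy or start of a prohibited AD/pruritus therapy, when it precedes a first MCID, as a competing event, and report the Aalen-Johansen cumulative incidence. State which date defines the competing event.
- Censor at the last score only for other reasons.
- Report the number of such exits with the curve.
- Keep the present Kaplan-Meier as a sensitivity analysis.

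Aalen-Johansen is preferable to simply carrying failures as event-free to Day 29. The two coincide only without other early censoring; in a run with 10 other dropouts, carrying failures forward gave 70.6% against 70.9%.

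The cost is a few lines of SAP text and a small derivation from the primary discontinuation reason, which Protocol 7.1.2 already requires in the eCRF. The medication record can supplement it if the reason categories do not separate these cases. The downside is a slightly lower reported attainment if such exits occur. If none occur, the result is unchanged.

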12.4 Other Analyses

12.4.1 Abbreviated 9-Item Treatment Satisfaction Questionnaire for Medication

The Abbreviated 9-Item Treatment Satisfaction Questionnaire for Medication (TSQM-9) is a 9-item measure that assesses the most common dimensions participants use to evaluate their medication (ie, global satisfaction, effectiveness, and convenience). The results for each scale (global satisfaction, effectiveness, and convenience) are presented from 0 to 100, where higher scores represent better satisfaction. Scoring method for each scale is presented in [Appendix 3](#).

TSQM-9 data for each scale will be summarized separately by visit using descriptive statistics. All TSQM-9 data will be listed.

12.4.2 Transepidermal Water Loss

Transepidermal water loss (TEWL) quantifies the clinical severity of AD and the associated effect on skin barrier function. Three TEWL readings are taken at each location (lesional and non-lesional), and the median will be calculated for these three readings. If the participant performs less than 3 readings, the median will still be calculated based on available readings. Descriptive statistics for the median of the three TEWL measurements will be presented by location and visit,

	STATISTICAL ANALYSIS PLAN, Version Final v1.0
Protocol Number: INCB 18424-901	Sponsor: Incyte Corporation
Study Title: An Open-Label, Single-Arm Study to Evaluate the Effect of Ruxolitinib 1.5% Cream on Itch in Adult Participants With Atopic Dermatitis (SCRATCH-AD)	

and the corresponding change from baseline when appropriate. The 95% CI will be provided for the mean change from baseline. All Transepidermal Water Loss measurements will be listed.

12.4.3 Eczema Area and Severity Index

The Eczema Area and Severity Index (EASI) is a composite score ranging from 0 to 72 that takes into account the degree of erythema, induration/infiltration (papules), excoriation, and lichenification (each scored from 0 to 3 separately) for each of 4 body regions, with adjustment for the percentage of BSA involved for each body region and for the proportion of the body region to the whole body. Scoring method for the Eczema Area and Severity Index is presented in [Appendix 4](#).

Descriptive statistics for the EASI will be presented by visit, and the corresponding change and percent change from baseline when appropriate. The 95% CI will be provided for the mean change and percent change.

Additionally, the proportion of participants with at least a 75% reduction from baseline in EASI (EASI-75) and associated 95% CI (using the Clopper-Pearson method) will be reported descriptively.

All EASI assessments will be listed. A line graph presenting the value in EASI and a line graph presenting the change from baseline in the EASI over time will be produced.

12.4.4 Total BSA Affected by AD

The overall BSA affected by AD (total BSA%) will be presented by visit, and the corresponding change and percent change from baseline when appropriate. The 95% CI will be provided for the mean change and percent change. All total BSA affected assessments will be listed. A line graph presenting the value and a line graph presenting the change from baseline in the total BSA affected over time will be produced.

13 SAFETY ANALYSIS

All safety analyses will be conducted using the safety analysis set.

13.1 Adverse Events

Adverse events (AEs) will be coded according to the Medical Dictionary for Regulatory Activities (MedDRA), Version 24.0.

Treatment emergent adverse events (TEAEs) are derived as any AEs with onset date during or after the first study treatment dose. AEs starting on the first study treatment dosing date and related

	STATISTICAL ANALYSIS PLAN, Version Final v1.0
Protocol Number: INCB 18424-901	Sponsor: Incyte Corporation
Study Title: An Open-Label, Single-Arm Study to Evaluate the Effect of Ruxolitinib 1.5% Cream on Itch in Adult Participants With Atopic Dermatitis (SCRATCH-AD)	

to a pre-dose study assessment will not be considered as TEAE. See [Appendix 2](#) for handling of completely or partially missing dates for AEs. In the case where it is not possible to define an AE as treatment emergent or not, the AE will be classified as treatment emergent.

An overall summary table of adverse events will be provided. The number of events and the number and percentage of participants who experienced AE, TEAE, TEAE at application site, TEAE by relationship, TEAE by toxicity grade, related TEAE by toxicity grade, TEAE of CTCAE Grade 3 or higher, serious TEAE, serious TEAE by toxicity grade, TEAE leading to study drug interruption, TEAE leading to study drug discontinuation, TEAE leading to study discontinuation and AE leading to death will be presented.

Unless otherwise specified, a participant experiencing the same TEAE multiple times will be counted only once for the corresponding PT. Similarly, if a participant experiences multiple TEAEs within the same SOC, the participant will be counted only once for that SOC. TEAEs will be sorted alphabetically by SOC and within each SOC the PT will be presented by decreasing order.

Frequency and percentage of participants who experience TEAE will be summarized by SOC and PT within SOC.

Frequency and percentage of participants who experience TEAE will be summarized by SOC, PT and relationship (causality). A treatment-related AE is defined as any TEAE that is assessed by the Investigator as possibly related to study treatment. TEAE that is assessed as not possibly related will be defined as not treatment-related. TEAE with an unknown relationship will be considered as treatment-related. If a participant experiences more than one TEAE within different relationship categories within the same SOC/PT, the participant will be counted once for that SOC/PT in each relationship category.

Frequency and percentage of participants who experience TEAE will be summarized by SOC, PT and intensity grade. TEAE with an unknown intensity grade will be considered missing. If a participant experiences more than one TEAE within different intensity grade categories within the same SOC/PT, the participant will be counted once for that SOC/PT in each intensity grade category. Similarly, frequency and percentage of participants who experience treatment-related TEAE will be summarized by SOC, PT and intensity grade.

Frequency and percentage of participants who experience serious TEAE will be summarized by SOC and PT within SOC.

Frequency and percentage of participants who experience TEAE of intensity of Grade 3 or higher will be summarized by SOC and PT within SOC.

Frequency and percentage of participants who experience serious TEAE will be summarized by SOC, PT and intensity grade. TEAE with an unknown intensity grade will be considered missing.

	STATISTICAL ANALYSIS PLAN, Version Final v1.0
Protocol Number: INCB 18424-901	Sponsor: Incyte Corporation
Study Title: An Open-Label, Single-Arm Study to Evaluate the Effect of Ruxolitinib 1.5% Cream on Itch in Adult Participants With Atopic Dermatitis (SCRATCH-AD)	

If a participant experiences more than one TEAE within different intensity grade categories within the same SOC/PT, the participant will be counted once for that SOC/PT in each intensity grade category.

Frequency and percentage of participants who experience Application Site TEAE will be summarized by SOC and PT.

Frequency and percentage of participants who experience TEAE of Application site pain Preferred Term will be summarized by Lowest Level Term.

Listings of all AEs, all AEs leading to death, all serious AEs, all TEAEs leading to study treatment discontinuation, all TEAEs leading to study treatment interruption and all TEAEs leading to study discontinuation will be provided. A listing of drug overdose will be provided.

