8.3.1. Adverse Events

Adverse events will be monitored from the time the participant signs the ICF until at least 15 (± 2) days after the last study drug application. Adverse events that begin or worsen after informed consent should be recorded on the Adverse Events Form in the eCRF regardless of the assumption of a causal relationship with the study drug. Conditions that were already present at the time of informed consent should be recorded on the Medical History Form in the eCRF. Adverse events (including laboratory abnormalities that constitute AEs) should be described using a diagnosis whenever possible rather than by individual underlying signs and symptoms.

Adverse events will be reported by the participant (or, when appropriate, by a caregiver, surrogate, or the participant's legally authorized representative). The investigator and any qualified designees are responsible for detecting, documenting, and recording events that meet the definition of an AE or SAE and remain responsible for following-up on AEs that are serious, considered related to the study drug/procedures, or that caused the participant to discontinue the study drug. Care will be taken not to introduce bias when detecting AEs and/or SAEs.

Open-ended and nonleading verbal questioning of the participant, such as "How are you feeling?" is the preferred method to inquire about AE occurrences. Adverse events may also be detected when they are volunteered by the participant during the screening process or between visits or through physical examinations, laboratory tests, or other assessments. The definition, reporting, and recording requirements for AEs are described in Section [9](#).

All SAEs will be reported to the sponsor or designee within 24 hours of the knowledge of the occurrence. The investigator will submit any updated SAE data to the sponsor within 24 hours of it being available.

After the initial AE/SAE report, the investigator is required to proactively follow each participant at subsequent visits/contacts. All SAEs will be followed until resolution, stabilization, the event is otherwise explained, or the participant is lost to follow-up (as defined in Section [7.3](#)).

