9.3. Recording and Follow-Up of Adverse Events and/or Serious Adverse Events

Adverse Event and Serious Adverse Event Recording

- An AE/SAE (including local and systemic reactions) that begins or worsens after informed consent is signed should be recorded on the Adverse Event Form in the eCRF. AEs/SAEs should be reported for enrolled participants, but only SAEs need to be reported for screen failure participants. For enrolled participants, conditions that were present at the time informed consent was given should be recorded on the Medical History Form in the eCRF. For detailed information refer to the eCRF guidelines.
- When an AE/SAE occurs, it is the responsibility of the investigator to review all documentation (eg, hospital progress notes, laboratory reports, and diagnostic reports) related to the event.
- The investigator (or delegate) will then record all relevant AE/SAE information in the eCRF.
- It is **not** acceptable for the investigator to send photocopies of the participant's medical records in lieu of completing the Adverse Event Form in the eCRF.
- There may be rare instances when copies of medical records for certain cases are requested. In this case, all participant identifiers, with the exception of the participant number, will be redacted by the site staff on the copies of the medical records before submission. These records can be submitted to Incyte Pharmacovigilance by email/fax per the contact information listed in the SRM.
- The investigator will attempt to establish a diagnosis of the event based on signs, symptoms, and/or other clinical information. Whenever possible, the diagnosis (not the individual signs/symptoms) will be documented as the AE/SAE. When a clear diagnosis cannot be identified, each sign or symptom should be reported as a separate AE/SAE.

To the extent possible, each AE/SAE should be evaluated to determine the following:

- The severity grade (CTCAE v5.0 Grade 1 to 5). See below for further instructions on the assessment of severity.
- Whether there is at least a reasonable possibility that the AE is related to the study drug: suspected (yes) or not suspected (no). See below for further instructions on the assessment of causality.
- The start and end dates, unless unresolved at the final safety follow-up visit.
- The action taken with regard to study drug as a result of the AE/SAE(s).

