- For each AE/SAE, the investigator **must** document in the medical notes that he/she has reviewed the AE/SAE and has provided an assessment of causality.
- With regard to assessing causality of SAEs:
 - There may be situations in which an SAE has occurred and the investigator has minimal information to include in the initial report. However, the causality assessment is one of the criteria used when determining regulatory reporting requirements. **Therefore, it is very important that the investigator always make an assessment of causality based on the available information for every event before the initial transmission of the SAE.**
 - The investigator may change his/her opinion of causality in light of follow-up information and submit the updated causality assessment.

Follow-Up of Adverse Events and Serious Adverse Events

- The investigator is obligated to perform or arrange for the conduct of supplemental measurements and/or evaluations as medically indicated or as requested by the sponsor to elucidate the nature and/or causality of the AE or SAE as fully as possible. This may include additional laboratory tests or investigations, histopathological examinations, or consultation with other health care professionals.
- Once an AE is detected, it should be followed in the AE eCRFs until it has resolved, has stabilized, or until it is judged to be permanent; assessment should be made at each visit (or more frequently if necessary) of any changes in severity, the suspected relationship to the study drug, the interventions required to treat the event, and the outcome.
- When the severity of an AE changes over time for a reporting period (eg, between visits), each change in severity will be reported as a separate AE.
- If a participant dies during participation in the study or during a recognized follow-up period, the investigator will provide the sponsor with a copy of any postmortem findings, including histopathology.
- Updated SAE information will be recorded in the originally completed eCRF and reported to Incyte Pharmacovigilance until resolution, stabilization, the event is otherwise explained, or the participant is lost to follow-up.
- Any updated SAE data (including SAEs being downgraded to nonserious) will be submitted to the sponsor (or designee) within 24 hours of receipt of the information.

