10.4.4. Safety Analyses

Safety analyses will be conducted for the safety population.

Adverse events (local and systemic) will be coded by the MedDRA dictionary, and TEAEs (ie, AEs reported for the first time or worsening of a pre-existing event after first application of study drug) will be tabulated by preferred term and system organ class for all events, related events, and events of Grade 3 or higher. Quantitative safety variables (eg, laboratory assessments, vital signs) and their changes from baseline will be summarized with descriptive statistics. Clinically notable abnormal values will be flagged and tabulated based on predefined criteria.

The clinical laboratory data will be analyzed using summary statistics. Descriptive statistics will be determined for vital signs. Vital sign results will be reviewed for clinically notable abnormalities.

Measures of exposure (eg, days of exposure, number of applications) to study drug will be summarized by means of summary statistics.

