3.5 Changes to the Analysis from the Protocol

No changes were made from the planned analysis in protocol.

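### The SAP's onset-date rule for treatment-emergent adverse events could count a pre-dose event that improves after Day 1, which the protocol's definition would not

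*SAP*

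**What the plan says.** - **SAP 13.1** defines TEAEs as "any AEs with onset date during or after the first study treatment dose". It does not compare the record with any pre-dose grade.
- **SAP 13.1, exception.** AEs are not treatment-emergent if they fall under "AEs starting on the first study treatment dosing date and related" to an assessment made before dosing. Where status cannot be determined, "the AE will be classified as treatment emergent".
- **Protocol 10.4.4** defines TEAEs as "AEs reported for the first time or worsening of a pre-existing event after first application of study drug".
- **Protocol 9.3** says that when the severity of an AE changes over a reporting period, "each change in severity will be reported as a separate AE". The sentence is not limited to worsening. The items to be evaluated for each AE include "The start and end dates, unless unresolved at the final safety follow-up visit".
- **Protocol 8.3.1** starts collection at consent: "Adverse events will be monitored from the time the participant signs the ICF". Pre-dose AEs of treated participants are therefore in the AE data.
- **SAP 3.5** states: "No changes were made from the planned analysis in protocol".

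Neither document gives a rule for linking a severity-change record to the earlier record of the same event.

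**The concern.** The two definitions differ and the difference is not declared. Under the protocol, a pre-existing event enters the TEAE tables only if it worsens after the first application. Under the SAP, what counts is when a record starts. Since a fall in severity also generates a record, an improving pre-dose event can pass the SAP's test while failing the protocol's.

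The incidence and severity of AEs is a secondary endpoint (Protocol Table 4; SAP 2), and there is no control arm in which the same artefact would show up for comparison. Screening can last up to 37 days, and current AD and itch treatments are stopped (Protocol 5.1, criterion 14; Table 8). An AE that starts before Day 1 and eases on treatment is therefore possible. If it were counted, an improvement would be tabulated as an emergent event.

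**Working it through.** The plan gives no figure on this point, so the check is to apply both rules to constructed cases and then scale the result.

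**Inputs.** SAP rule: record onset on or after first dose (SAP 13.1). Protocol rule: first report, or worsening, after first application (Protocol 10.4.4). Separate record for each severity change (Protocol 9.3). Planned number: about 48 (Protocol 4.1; SAP 3.1).

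**Assumption.** The new record's onset is the date of the severity change. This is the natural reading of a separate AE with its own start date, but it is not stated.

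**Constructed case.** A headache starts on Day -5 at Grade 2, falls to Grade 1 on Day 4 and resolves on Day 9.

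| Record | Grade | Onset | SAP 13.1 | Protocol 10.4.4 |
|---|---|---|---|---|
| 1 | 2 | Day -5 | not a TEAE | not a TEAE |
| 2 | 1 | Day 4 | TEAE | not a TEAE (neither new nor worse) |
| Total | | | 1 | 0 |

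**Mirror case.** If the event rises from Grade 1 to Grade 2 on Day 4, both rules give one TEAE. So under this dating assumption the SAP captures worsening, and the discrepancy is over-inclusion only.

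**Do other SAP rules remove record 2?**
- The Day 1 exception does not reach it, because its onset is Day 4.
- Counting a participant once per preferred term operates among TEAEs. Record 1 is not a TEAE, so record 2 is the one counted.
- The default for undeterminable cases classes events as treatment-emergent, so it cannot remove the record.

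Record 2 would therefore appear in the overall TEAE summary, the SOC/PT table, and the tables by relationship and by grade.

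**Conditions.** The event must be Grade 2 or higher before dosing, still ongoing at Day 1, and must then fall to a lower non-zero grade. A Grade 1 event can only resolve, and resolution should produce no new graded record.

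**Scale.** Assume all 48 are in the safety set, and let k be the number of participants whose only TEAE is such a record. The rise in overall TEAE incidence is 100 × k/48:
- k = 1: 2.1 percentage points
- k = 2: 4.2
- k = 3: 6.3

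A participant with another TEAE adds 0 to overall incidence. A participant with another TEAE of the same preferred term also adds 0 at that preferred-term level, although the event count can still rise.

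**The case against.** **The onset date of the new record is not stated.** Protocol 9.3 refers to eCRF guidelines that are not among the documents. If a follow-on record kept the event's first onset date, an improving pre-dose event would stay pre-treatment. This stands, and it makes the miscount conditional. It does not rescue the SAP wording, though: under that convention a pre-dose event that worsened after Day 1 would also keep a pre-dose onset, and the SAP rule would miss it, contrary to protocol 10.4.4.

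**The severity sentence may not be meant for improvement.** Protocol 8.3.1 and 9.3 direct sites to record events that begin or worsen after consent. Protocol 9.3 also has AEs followed until they resolve or stabilise and lists recovering/resolving as an outcome, so improvement could be handled inside the existing record. This is a fair alternative reading, but the sentence itself covers any change, and sites may apply it literally.

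**AD flare and itch during washout are not automatically AEs.** A reader might infer that many participants will have such events. The documents do not support that. Conditions present at consent go to medical history, and protocol 9.1 makes expected fluctuation of a pre-existing condition reportable only if it is worse than expected. An unusual exacerbation in screening can still qualify, but its frequency is not known.

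**Related harm.** A reader might also infer that benefit would be tabulated as drug-related. Causality is the investigator's judgment and needs evidence suggesting a causal link (Protocol 9.3). An event that began before dosing and then eased is an unlikely candidate, so that inference is speculation.

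**Impact.** The error runs towards over-counting harm, the study is descriptive with no formal comparisons (Protocol 10.3; SAP 5.6), and all AEs are listed. This limits the consequence. It does not remove the undeclared conflict between the two definitions.

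**Conclusion.** The definitions in SAP 13.1 and protocol 10.4.4 differ, and SAP 3.5 says that nothing changed. Together with the separate-record rule in protocol 9.3, the SAP wording could count an improving pre-dose AE as a TEAE. That conclusion rests on the new record carrying the date of the change as its onset, and on sites creating a record for improvement.

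The number of participants affected cannot be known from the documents and is probably small. The figure of about 2.1 percentage points applies only to a participant whose sole TEAE is such a record, with all 48 in the safety set. It is tempting to read it as the effect of every such record, but a participant with any other TEAE leaves overall incidence unchanged.

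The correction is worth making because it is cheap, it restores the protocol's definition, and it protects a secondary safety endpoint in a study with no control arm.

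**What to change.** In SAP 13.1, define a TEAE as either (a) an AE first occurring on or after the first application, or (b) a severity-change record, dated on or after the first application, whose CTCAE grade exceeds the linked event's pre-dose grade. Records that continue a pre-dose AE at the same or a lower grade are listed but not counted as TEAEs.

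Specify the reference grade, because the choice can change the result. Take an event that was Grade 3 in screening, Grade 1 at first application and Grade 2 on treatment. It is a TEAE against the last grade before first application, but not against the highest pre-dose grade. Either can be defended if fixed before database lock.

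State in the SAP which date serves as the onset of a severity-change record, in agreement with the eCRF guidelines. If the onset-date rule is kept on purpose, declare it in SAP 3.5 as a departure from protocol 10.4.4.

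The cost is one SAP sentence and the programming to link consecutive records of the same event. No extra data collection is needed, provided that successive records can be matched from the AE data.
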